The objective of this pilot study is to determine if an experimental mouth rinse and a marketed dry mouth rinse are more effective in relieving dry mouth (as determined by the response to “relieving the discomfort of dry mouth” question from the modified Product Performance and Attributes Questionnaire I/ Moisturization and Dryness (PPAQ I/ MD)) compared to water.

2. Overall Study Design and Plan

This is a controlled, randomized, 3-treatment, 3-period crossover study in subjects with self-reported dry mouth symptoms as determined by subject responses to the Dry Mouth Inventory (DMI). A sufficient number of volunteers will be screened to ensure enrollment of up to 30 subjects at Acclimation. Subjects who meet the eligibility criteria will continue into the treatment phase of the study. Safety will be assessed by Oral examinations at Baseline/Day1 and Day 4. Subjects will complete questionnaires at Baseline (before product use Day 1 only), after immediate use, 30 minutes, 1 hour, 2 hours, and 4 hours after supervised product use on Day 1 and Day 4 of each period. The PPAQ II questionnaire will be completed in the morning of Day 4 of each period. Subjects will be randomly assigned to treatment sequences at the Baseline visit of Period 1. The treatment and washout periods will be repeated until all three treatment periods have been completed.

Table 1. Study Schedule by Procedure Type and Visit

Procedures	Screening/ Acclimation	Treatment Periods 1, 2, & 3					Washout
		Day 1 On site	Day 1 Off Site	Days 2 & 3 At Home	Day 4 On site	Day 4 Off Site	
Informed Consent	X						
Medical History	X						
Demographics	X						
DMI Questionnaire	X						
Inclusion/Exclusion	X						
Acclimation/Washout Product Distribution	X						
PPAQ II Questionnaire					X*		
Continuance Criteria		X			X		
Baseline MD Questionnaire		X					
Oral Examination		X			X		
Assigned Rinse / Water Product Distribution		X					
Supervised AM Product Use		X			X		
Immediate MD Questionnaire		X			X		
Product Usage Questionnaire		X**					
PPAQ I/ MD Questionnaire- 30 minutes		X			X		
PPAQ I/ MD Questionnaire- 1 hour			X			X	
PPAQ I/ MD Questionnaire- 2 hour			X			X	
PPAQ I/ MD Questionnaire- 4 hour			X			X	
4-hour Rating Questionnaire			X			X	

Product Diary		X	X	X	X		
Product Diary Return					X		
Treatment Product Return					X		
General Comments	X	X			X		
AEs		X			X		
Subject Accountability					X***		

* PPAQ II will be completed at home immediately after wake-up; **This questionnaire will be analyzed outside of this protocol

***P3-Day 4 only or when subject is dismissed from study.

Screening/Acclimation Visit

At the site, up to forty subjects will be asked to read and sign an informed consent form and will receive a signed copy for their records. Personal medical history information will be reviewed and retained as site source documentation. Demographic information will be recorded, and subjects will answer the DMI questionnaire to ensure study eligibility. Entrance criteria will be assessed. At total of thirty qualifying subjects will receive acclimation products and usage instructions. Subjects continuing will begin using these products in place of their normal oral hygiene products for the duration of the study. They will be instructed to brush their teeth in the morning of Day 1 visit. Subjects not meeting study entrance criteria will be dismissed.

Treatment Visits, Periods 1-3

Day 1 On-site Visit

Continuance criteria will be assessed. Subjects will complete a Baseline MD Questionnaire, followed by an oral examination. Subjects will then be randomly assigned to a treatment sequence (Period 1 only). Assigned treatment product kit boxes will be distributed, written instructions reviewed, and subjects will use the assigned products for the first time under supervision by site staff. A timer will be set for 4 hours and subjects will be instructed to refrain from eating, drinking, smoking, using their test products, using tobacco, using a medicated lozenge, chewing gum, or breath mints during the 4-hour time period. Immediately following product use, subjects will complete an Immediate MD Questionnaire and Product Usage Questionnaire (analyzed outside of this protocol). Subjects will remain on-site for the first 30 minutes to complete the PPAQ I/ MD 30-minute Questionnaire. Subjects will be instructed to complete PPAQ I/ MD at 1-hour, 2-hour and 4-hour and to fill out the 4-hour Rating Questionnaire at 4-hour. Subjects who received rinse products will be reminded to use them at least one more time (up to 5 times daily) after the last 4-hour questionnaire for Day 1 has been completed. Subjects will be reminded to bring their treatment boxes to their next study visit, and to refrain from using any rinse product the morning of their site visit.

Day 1 Off-site

Subjects will complete questionnaires, PPAQ I/ MD, at 1-hour (Day 1 PPAQ I/ MD 1h), 2-hour (Day 1 PPAQ I/ MD 2h), 4-hours (Day 1 PPAQ I/ MD 4h), and a 4-hour Day 1 Rating Questionnaire. Subjects will refrain from eating, drinking, smoking, using tobacco, using a medicated lozenge, chewing gum, or breath mints during the 4-hour time period until the last questionnaire for Day 1 has been completed.

All subjects will fill out a product diary tracking their product usage.

Days 2 and 3 At-home

Subjects will use the toothpaste products at home twice a day. Subjects that were assigned to the rinse products should use the rinse at least twice a day (no more than 5 times a day). All subjects will fill out a product diary tracking their product usage. Subjects will be reminded to follow the restrictions listed on the usage instructions. There is no eating or drinking restrictions for Day 2 and Day 3. Subjects from all groups will be allowed to sip unlimited amount of water.

Day 4 On-site Visit

Before coming to the site, subjects will complete a PPAQ II questionnaire (this questionnaire should be completed immediately after waking up). Subjects will also be sent a reminder to brush but not to use the assigned rinse product the morning, and to bring treatment products and the completed PPAQ II to their next site visit. Continuance criteria will be assessed, and take-home rinse products, product diaries and completed PPAQ II will be collected. An oral examination will be performed. After the oral exam, subjects will use the assigned products under supervision by site staff. A timer will be set for 4 hours. Subjects will remain on-site to complete the Immediate MD questionnaire and the 30-minute questionnaire (Day 4 PPAQ I/ MD 30 min). Subjects will be instructed to complete (Off-site) PPAQ I/ MD at 1-hour, 2-hour and 4-hour and to fill out the 4-hour Rating Questionnaire at 4-hour.

At this visit site staff will remind the subjects to refrain from eating, drinking, smoking, using any oral care products, using tobacco, using a medicated lozenge, chewing gum, or breath mints during the 4-hour time period. Subjects will be reminded to follow the restrictions listed on the usage instructions.

At Period 3 Day 4 washout product will be collected.

Day 4 Off-site

Subjects will complete a questionnaire, PPAQ I/ MD, at 1-hour (Day 4 PPAQ I/ MD 1h), 2-hours (Day 4 PPAQ I/ MD 2h), 4-hours (Day 4 PPAQ I/ MD 4h), and the 4-hour Day 4 Rating Questionnaire. After the Day 4, 4-hour questionnaires are completed, subjects will continue to use the study toothpaste for the wash-out period. Subjects will refrain from eating, drinking, smoking, using any oral care products, using tobacco, using a medicated lozenge, chewing gum, or breath mints during the 4-hour time period until the last questionnaire for Day 4 has been completed.

After the Period 3 Day 4 4-hour questionnaires have been completed, the subject will be dismissed from the study, and a Subject Accountability form will be completed.

Throughout the Study

General comments can be recorded at any time during the study. All Adverse Events (AEs) will be recorded. Any subject reported AE that remains unresolved by the end of the study should be followed up until resolution by the investigator/designee, and the resolution should be documented only as source documentation. If a subject is unreachable to determine whether the AE has been resolved, the attempts to contact the subject should be documented as source documentation. If, for any reason, a subject does not complete the study, an explanation will be entered on the Subject Accountability CRF. All data gathered on the subject prior to discontinuation will be made available to the Sponsor.

3. Inclusion Criteria

In order to be included in the study, each subject must:

- Provide written informed consent prior to participation and be given a signed copy of the informed consent form;
- Be at least 18 years of age;
- Be in good general health as determined by the Investigator/designee;
- Agree not to participate in any other oral care studies for the duration of this study;
- Agree to delay elective dentistry, including dental prophylaxis, until study completion, and to report any non-study dentistry received during the course of the study;
- Agree to refrain from the use of any non-study oral hygiene products for the study duration including mouth rinse and toothpaste (flossing is permitted if part of their normal routine);

- Self-report a dry mouth feeling according to the modified DMI questions. (Subject must answer at least 2 out of 4 questions with 'agree a little,' 'agree' or 'strongly agree');
- Agree to refrain from eating, drinking, smoking, using oral care products, using tobacco, using a medicated lozenge, chewing gum, or breath mints during the 4-hour test period;
- Agree to return for all scheduled visits and to follow all study procedures.

4. Exclusion Criteria

Subjects will be excluded from study participation where there is evidence of:

- Any condition or disease, as determined by the Investigator/Designee, that could be expected to interfere with examination procedures, with compliance, or with the subject's safe completion of the study;
- Severe periodontal disease, as characterized by purulent exudate, generalized mobility, and/or severe recession;
- Active treatment for periodontitis;
- Having a history of allergies or hypersensitivity to mouth rinse or ingredients in commercial dental products or cosmetics;
- Self-reported pregnancy or the intent to become pregnant during the study, or breast feeding;
- Full or partial dentures or any orthodontic appliances such as braces or aligners, or tongue or mouth piercing;
- Having diabetes;
- Inability to undergo any study procedure;
- Having untreated oral mucosal disease which in the opinion of the investigator could interfere with the study (e.g., current oral ulceration);
- Use of prescription systemic parasympathetic medications (e.g., Pilocarpine), for the treatment of the feeling of dry mouth;
- Currently under the care of a dental/medical professional specifically for the treatment of dry mouth (*at the discretion of the Investigator/Designee*);
- Self-reported mouth breathers (i.e., mouth breathing secondary to nasal obstruction);
- Evidence of gross intra-oral neglect or need for extensive dental therapy; or
- Currently undergoing radiotherapy and/or chemotherapy treatment.

5. Continuance Criteria

Subjects may be excluded from the study or the analysis if they:

- Have participated in any other oral care study since the last study visit;
- Since the last study visit, have developed any condition or disease or taken a new medication, which as determined by the Investigator/Designee could be expected to interfere with examination procedures, with compliance, or with the subject's safe completion of the study;
- Used any non-study oral hygiene products since the last study visit;
- Used study mouth rinse the morning of the study visit (*Day 4 only*); or
- Had any non-study dentistry, including dental prophylaxis performed since the last study visit.

6. Identity of Investigational Product(s)

- Acclimation/Washout: Burt's Bees Enamel Care Toothpaste (0.243% sodium fluoride, 0.13% w/v fluoride ion) and an Oral-B Indicator toothbrush
- Group 1: Burt's Bees Enamel Care Toothpaste (0.243% sodium fluoride, 0.13% w/v fluoride ion), Biotene Dry Mouth rinse (Purified Water, Glycerin, Xylitol, Sorbitol, Propylene Glycol, Poloxamer 407, Sodium Benzoate, Hydroxyethyl Cellulose, Methylparaben, Propylparaben, Flavor, Sodium Phosphate, Disodium Phosphate), and an Oral-B Indicator toothbrush
- Group 2: Burt's Bees Enamel Care Toothpaste (0.243% sodium fluoride, 0.13% w/v fluoride ion), Experimental mouth rinse (0.1% Sodium Hyaluronate), and an Oral-B Indicator toothbrush
- Group 3: Burt's Bees Enamel Care Toothpaste (0.243% sodium fluoride, 0.13% w/v fluoride ion), 15ml of water (on-site only) and an Oral-B Indicator toothbrush

7. Product Usage

At-home Toothpaste

Subjects will brush their teeth thoroughly, twice daily (morning and evening) as they normally do with the provided toothpaste and toothbrush. Subjects will be asked to use this toothpaste and toothbrush for the duration of the study, for both the acclimation/washout and treatment periods. Flossing and tongue brushing are permitted during the study if it is part of their normal routine.

Group 1 - Marketed rinse

On-site: Subjects will rinse their mouth with the assigned mouth rinse 15 ml for 30 seconds. Subjects will record usage in their product diaries. Subjects will not be allowed to use any mouth rinse during the 4-hour time period on Day 1 and Day 4.

At-home: Subjects will be instructed to use the rinse products at least twice a day and up to 5 times a day including any on-site usage, 15 ml for 30 seconds. Rinse can be used alone or after each time subjects brush. Subjects will record the usage in their product diaries.

Group 2 - Experimental mouth rinse

On-site: Subjects will rinse their mouth with the assigned mouth rinse 15 ml for 30 seconds. Subjects will record usage in their product diaries. Subjects will not be allowed to use any mouth rinse during the 4-hour time period on Day 1 and Day 4.

At-home: Subjects will be instructed to use the rinse products at least twice a day and to 5 times a day including any on-site usage, 15 ml for 30 seconds. Rinse can be used alone or after each time subjects brush. Subjects will record the usage in their product diaries.

Group 3 – Water/ No Rinse

On-site: Subjects will take, all at one time, a 15ml sip of water.

At-home: Subjects will continue brushing with provided washout toothpaste. Subjects will not be allowed to use any mouth rinse. Subjects will record their toothpaste usage in their product diaries.

8. Blinding, Labeling, and Shipping Plan

Acclimation/Washout take-home kit boxes will be labeled with study number, emergency phone number, distributor name/address, appropriate caution statements, content statement and other information as required by internal regulations and clinical SOPs. Treatment take-home kit boxes will be identically sized and labeled with a unique kit box number or code, study number, emergency phone number, distributor name/address, appropriate caution statements, content statement and other information as required by internal regulations and clinical SOPs. The shipping containers will be labeled with the clinical site address and a content statement listing study number and kit box numbers contained within. The site will be provided with a randomization treatment sequence and supplemental product.

The site will be provided with a code breaker report in a sealed envelope. The sealed code breaker report contains documents that list the kit box number or treatment code while the identity of the treatment products is hidden by an opaque scratch-off seal. If the study blind needs to be broken, an individual subject's investigational product may be ascertained by opening the sealed code breaker report, locating the subject's kit box number or treatment code and scratching off the opaque seal to reveal the treatment identity. The sealed code breaker report will be opened if a clinically serious AE occurs or management of the subject requires knowledge of the identity of the investigational product. The Investigator should immediately inform the Sponsor that the code will be broken and record the date, time and reason for breaking the code in writing. After the study is complete and the study database has been finalized and locked, the site will return the code breaker report to the Sponsor using the self-addressed, stamped envelope provided by the Sponsor.

9. Method of Assigning Subjects to Treatment Groups

Study Design	N	# of Treatments	# of Periods	Treatment Sequences	Number of Subjects Per Sequence
Crossover	30	3	3	ABC, ACB, BAC, BCA, CAB, CBA	5-6

Treatment Sequence Schedule

Each of the eligible subjects will be randomly assigned to one of the treatment sequences. Subjects will be assigned to a treatment sequence in the order they come to the site during their first Baseline visit using a Treatment Sequence Schedule. The site will keep the Treatment Sequence Schedule while the study is on-going. Should a subject miss a treatment period, that treatment in the sequence will be skipped.

10. Determination of Sample Size

Sample size is based on logistical considerations.

11. Safety Variables

Oral Examination

Assessment of the oral soft tissue is conducted via a visual examination of the oral cavity and perioral area utilizing a standard dental light, dental mirror, and gauze. The structures examined include the gingiva (free and attached), hard and soft palate, oropharynx/uvula, buccal mucosa, tongue, floor of the mouth, labial mucosa, mucobuccal/mucolabial folds, lips, and perioral area.

Assessment of the oral hard tissues are conducted via a visual examination of the dentition and restorations utilizing a standard dental light, dental mirror, and air syringe. All abnormal findings are recorded and categorized by their location with hard tissue findings categorized as “other-oral.” An AE is recorded if a new abnormal finding is noted after treatment application or any abnormal finding noted prior to treatment application increases in severity after treatment is applied.

12. Hypotheses

The following hypotheses will be tested for each response to the PPAQ I/ MD questions, the PPAQ II questions, and the rating questions at each applicable time point:

Null: The mean response is equal between the Experimental rinse and Water.

Alternative: The mean response is not equal between the Experimental rinse and Water.

Null: The mean response is equal between the Marketed rinse and Water.

Alternative: The mean response is not equal between the Marketed rinse and Water.

The primary endpoint will be the response to “relieving the discomfort of dry mouth” from the modified PPAQ I/ MD two hours after supervised product use on Day 4 of treatment. Responses to all other questions and time points will be of secondary interest.

13. Statistical and Analytical Plans

Responses to the questions will be analyzed separately using a general linear mixed model for a crossover with period and treatment as fixed effects and subject as a random effect. Carryover will be assessed and if reasonably appropriate, it may be included in the statistical model. Statistical comparisons will be two-sided with a significance level of 0.10. No adjustments will be made for multiple comparisons. Additional analyses of the data may be performed. This may include but is not limited to area under the curve (AUC).

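### Does leaving the carryover term to the analyst's judgement undermine the 0.10 level of the primary comparison?

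*Combined protocol and SAP*

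**What the plan says.** Section 13 (Statistical and Analytical Plans) analyses each question with a "general linear mixed model for a crossover with period and treatment as fixed effects and subject as a random effect". It then adds: "Carryover will be assessed and if reasonably appropriate, it may be included in the statistical model". The same paragraph sets the test level, "Statistical comparisons will be two-sided with a significance level of 0.10", and says "No adjustments will be made for multiple comparisons".

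Section 12 (Hypotheses) compares each rinse with water. It makes the relief item primary, read "two hours after supervised product use on Day 4 of treatment"; all other items and times are secondary.

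Section 9 uses all six orders, "ABC, ACB, BAC, BCA, CAB, CBA", with 30 subjects planned. It also states: "Should a subject miss a treatment period, that treatment in the sequence will be skipped". Section 2 places a washout between periods, and on Day 1 of each period, before the product is used, "Subjects will complete a Baseline MD Questionnaire, followed by an oral examination". Section 10 says that the sample size rests on logistics; there is no power calculation.

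**The concern.** Section 13 gives no test, threshold, form of term or time of decision for carryover, and does not say which model is primary if two are fitted. An analyst could fit both to the relief item, look at both results, and then judge whether the term was appropriate.

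Choosing a model on the data being tested is a known way to lose the nominal level. In this design the carryover estimate is uncorrelated with the treatment estimate from the model without the term, but correlated at 0.45 with the estimate from the model with it. If the term enters only when carryover looks large, the adjusted test is no longer a 0.10 test. The two models can also disagree on significance, and the plan does not say which answer counts. Finally, the carryover value after a skipped period is not defined. At stake is whether the 0.10 describes the primary test that is reported.

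**Working it through.** **Inputs from the documents.** Three treatments, three periods, six sequences and 30 subjects, taken as 5 per sequence (Section 9); two-sided 0.10 and the model (Section 13); rinse against water (Section 12).

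**Assumptions, because the documents give no figures.** Complete data; normal errors with within-subject variance σ²; first-order carryover, equal for both rinses and zero for water; carryover judged by a joint 2-df F test on the same outcome. Carryover and treatment effects are in within-subject SDs. Subject is fitted as a fixed effect.

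**1. The stated level.** There are 30 × 3 = 90 observations. Without carryover, residual df = 90 − 30 − 2 − 2 = 56 and the variance of a rinse–water difference is 2σ²/30 = 0.0667σ². With two carryover terms, df = 54 and the variance is 0.0833σ², a ratio of 1.25 (1.20 to 1.25 with subject random). Either model, fixed in advance and with no true carryover, reproduces 0.10: simulated 0.0995 and 0.0994 (400,000 trials, Monte Carlo SE about 0.0005).

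**2. Bias if the term is left out.** Each treatment is given 10 times in Period 1 and 10 times after each of the other two. If both rinses carry over c, a rinse mean gains 10c/30 = c/3 and the water mean gains 20c/30 = 2c/3. The difference is biased by −c/3, against the rinse.

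**3. Why selection matters.** The adjusted estimate equals the unadjusted one plus one third of the estimated carryover difference, and those two parts are uncorrelated. The correlation of the adjusted estimate with carryover is therefore √[(0.0833 − 0.0667)/0.0833] = √0.20 = 0.447.

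**4. Error with no true carryover.**
- Pre-test at 0.05, 0.10 and 0.20: 0.105, 0.108 and 0.112. Separate runs reach 0.113 at most.
- Smaller of the two p-values: 0.136 (0.134 to 0.138 across runs).
- Responses rounded to the 1–5 scale: 0.106, 0.109 and 0.112 for the pre-tests, and 0.137 for the smaller p. With 4 per sequence: 0.107, 0.110, 0.114 and 0.138.
- When the term enters at the 0.10 threshold, the conditional error is about 0.19. That happens in about 10% of trials, so it supplies only 0.10 × 0.19 = 0.019 of the total.

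**5. Error with true carryover from both rinses** (100,000 trials per row; separate runs agree within about 0.003).

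| Carryover (SD) | No term, fixed | Pre-test at 0.10 | Term, fixed |
|---|---|---|---|
| 0.25 | 0.115 | 0.124 | 0.100 |
| 0.5 | 0.160 | 0.149 | 0.099 |
| 0.75 | 0.228 | 0.155 | 0.100 |
| 1.0 | 0.311 | 0.135 | 0.100 |

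Hand check of 0.160: the bias in standard errors is (0.5/3)/√0.0667 = 0.645. With a critical value of 1.673, the normal approximation gives P(Z > 1.028) + P(Z < −2.318) ≈ 0.152 + 0.010 = 0.162.

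The largest rates sit in the second column. They come from fixing the model without the term, not from leaving the choice open.

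**6. Power for a 0.5 SD effect.** With no carryover, the effect is 0.5/√0.0667 = 1.94 standard errors without the term and 0.5/√0.0833 = 1.73 with it. Power is 0.61 and 0.53; the pre-test keeps about 0.60. With 0.5 SD carryover, the two fixed models give 0.34 and 0.52.

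**7. Direction.** The objective is whether the rinses do better than water. Under the 0.10 pre-test, the false rinse-better rate is 0.054 with no carryover and 0.040 to 0.051 for carryover of 0.1 to 1.0 SD, against 0.05 nominal. From 0.25 SD upward, essentially all of the excess is false findings in favour of water. The plan tests two-sided, so this adds to the two-sided totals and does not replace them.

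**The case for a change.** The strongest case for a change does not rest on the one-point inflation. At the 0.10 level the two models disagree in about 7% of null trials, and in 16% when the true effect is 0.5 SD, with nothing to say which counts. Deliberate choice of the smaller p gives about 0.137 with no carryover and about 0.20 when carryover is 0.5 SD. At 0.25 SD an honest pre-test (0.124) does worse than either fixed model. A sentence naming the primary model would cost almost nothing. The Baseline MD scores cannot settle the matter, since they cover moistness and dryness, not the relief item.

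All of that stands as arithmetic, but it does not carry far. Section 13 already states a default model, and a reader would take it as primary unless told otherwise. The 0.137 and 0.20 need someone to choose on the p-value, which the plan does not propose; even the pre-test is an assumed reading, because Section 13 does not say that carryover is judged by a significance test. Fixing the model without the term does worse than the pre-test from 0.5 SD upward. Fixing the model with it gives up about eight points of power (0.61 to 0.53) if the washout works. Which is preferable depends on how likely carryover is. The primary reading follows a washout and then the new period's regimen from Day 1 to Day 4, so large carryover has not been shown to be plausible. I found no washout length, but the text available was incomplete and I draw nothing from that.

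Coding the term after a skipped period is a detail that the analyst settles when fitting the model. No effect on the result has been shown.

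**Conclusion.** The wording is loose, but no change is needed. If the term is admitted by a test and there is no true carryover, the two-sided error for one rinse–water comparison is about 0.105 to 0.113 in place of 0.10; about 0.137 is the bound under deliberate selection. Where carryover is 0.5 SD or more, the flexible rule has lower error than a fixed model without the term. Where there is none, it has more power than a fixed model with it (about 0.60 against 0.53). Neither fixed model dominates what is written, so this is a trade-off plus a detail that a sensible analyst fills by treating the stated period–treatment–subject model as primary and showing the carryover model beside it. That primary model relies on an effective washout.

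The setting supports the same conclusion: a pilot sized by logistics, tested at 0.10 with no multiplicity adjustment across two comparisons and many items and times, does not claim strict error control. The figures rest on complete data from 30 subjects, first-order carryover, and assumed thresholds and carryover sizes that the documents do not give.
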